7.2 NULL AND ALTERNATIVE HYPOTHESES

The relative bioavailability of the different dose groups will be estimated by the ratios of the geometric means (test/reference) for the primary and secondary PK endpoints. Additionally, their two-sided 90% confidence intervals (CIs) will be provided. This method corresponds to the two one-sided t-tests procedure, each at the 5% significance level. Since the main focus is on estimation and not testing, an acceptance range was not specified, that is, no hypothesis will be tested.

7.3 PLANNED ANALYSES

7.3.1 Primary analyses

The pharmacokinetic endpoints listed in [Section 5.5.1](#) will be calculated according to the BI Standard Operating Procedure (SOP) 'Standards and processes for analyses performed within Clinical Pharmacokinetics/Pharmacodynamics' [[001-MCS-36-472](#)].

Plasma concentration data and parameters of a subject will be included in the statistical pharmacokinetic (PK) analyses if they are not flagged for exclusion due to a protocol violation relevant to the evaluation of PK (to be decided no later than in the Report Planning Meeting) or due to PK non-evaluability (as revealed during data analysis, based on the criteria specified below). Exclusion of a subject's data will be documented in the clinical trial report.

Relevant protocol violations may be:

- Incorrect trial medication taken, that is, the subject received at least one dose of trial medication the subject was not assigned to
- Incorrect dose of trial medication taken
- Use of restricted medications

Plasma concentrations and/or parameters of a subject will be considered as non-evaluable, if for example:

- The subject experiences emesis that occurred at or before 2 times median tmax of the respective treatment (median tmax is to be determined excluding the subjects experiencing emesis)
- A predose concentration is >5% Cmax value of that subject
- Missing samples/concentration data at important phases of PK disposition curve

The following analysis sets will be defined for this trial:

- Treated set (TS):
This subject set includes all subjects from the RS who were documented to have received one dose of study drug. This is the full analysis set population in the sense of ICH-E9
- Pharmacokinetic parameter set (PKS):
This subject set includes all subjects in the TS who provide at least one primary or secondary PK parameter that was not excluded according to the description above. Thus, a subject will be included in the PKS even if he/she contributes only one PK parameter value for one period to the statistical assessment

Point estimates of the ratios of the geometric means (test/reference) for the primary and secondary endpoints (see [Sections 5.5.1.1](#) and [5.5.1.2](#)), and their two-sided 90% confidence intervals (CIs) will be provided.

To this end, the PK endpoints will be log transformed (natural logarithm) prior to fitting the ANOVA model (cf. [Section 7.1.3](#)). For each endpoint, the difference between the expected means for $\log(T)-\log(R)$ will be estimated by the difference in the corresponding adjusted means (Least Squares Means), and a two-sided 90% confidence interval based on the t-distribution will be computed. These quantities will then be back-transformed to the original scale to provide the point estimate and 90% CIs for each endpoint.

The comparisons of interest will be T1 vs. R, T2 vs. R, and T3 vs. R. Further comparisons may be investigated if appropriate (e.g. T1 vs. T2) and will be described in the TSAP.

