4.1.4 Drug assignment and administration of doses for each subject

The treatments to be evaluated are as outlined in [Table 4.1.4: 1](#). Each subject will receive one single dose of trial medication. For further details concerning timing, see the [Flow Chart](#). Detailed instructions for the preparation of the SC injection solutions are provided in the ISF.

Table 4.1.4: 1 Dosage and treatment schedule

Dose Group	Total dose	Route of administration	Concentration of application solution	Application volume	Injection site
1		SC			Perumbilical
2		SC			Perumbilical (left and right)
3		SC			Perumbilical (left and right)
4		SC			Thigh

Following an overnight fast of at least 10 hours, the medication will be administered. Trial drug will be injected subcutaneously in the abdominal region or into the thigh. Detailed handling instructions will be provided in the ISF. Subjects will be kept under close medical surveillance until 48 hours following drug administration. For restrictions with regard to diet, see [Section 4.2.2.2](#).

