#### **4. CHANGES IN THE PLANNED ANALYSIS OF THE STUDY**

All analyses described in this TSAP are in accordance with the statistical methods described in the CTP.

CTP Section 7.3.1 states that the TS includes all subjects from the “RS” who were documented to have received one dose of study drug. “RS” was not explained, but in this context certainly refers to a randomized set. Since there is no randomization in this trial, it is clear that there is no randomized set and this must be a typo in the CTP and that the CTP actually intends the TS to include all subjects who were documented to have received one dose of study drug. The TS was defined in this TSAP accordingly, and this was considered to be in accordance with the intention of the CTP (despite of the typo).

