### 6.3 SUBJECT SETS ANALYSED

All entered subjects who received study medication will be included in the safety analysis and in the PK analysis depending on the availability of measurement values, and on their adherence to the CTP.

The following subject sets will be defined for statistical analysis:

- Treated set (TS):  
This subject set includes all subjects who received at least one dose of study drug. This is the full analysis set population in the sense of ICH-E9 (1). It will be used for analysis of safety, demographic data and baseline characteristics.
- Pharmacokinetic parameter set (PKS):  
This subject set includes all subjects in the TS who provide at least one primary or secondary PK parameter that was not excluded because of IPDs relevant to the statistical evaluation of PK endpoints, or because of non-evaluability, as described in Section 7.3.1 of the CTP. The discussion of all exceptional cases and problems and the decisions on the allocation of subjects to analysis sets will be made at latest at the RPM. These decisions will be documented in the decision log.

Table 6.3: 1 Subject sets analysed

Class of endpoint	Subject set	
	TS	PKS
Disposition	X	
Exposure	X	
IPDs	X	
Demographic/baseline characteristics	X	
Safety parameters	X	
Primary PK endpoints		X
Secondary PK endpoint		X
Further PK endpoints		X

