### Exclusion of PK parameters

The ADS ADPP contains column variables APEXC and APEXCO indicating inclusion/exclusion (APEXC) of a PK parameter and an analysis flag comment (APEXCO). All analyses based on the PKS are based on PK parameter values which are not flagged for exclusion, i.e. with APEXC equal to 'Included'.

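### Vomiting is a listed ground for discarding PK data although every dose is a subcutaneous injection

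*Protocol*

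**What the plan says.** Protocol section 7.3.1 opens its list of non-evaluability criteria with "Plasma concentrations and/or parameters of a subject will be considered as non-evaluable, if for example". The first item is "The subject experiences emesis that occurred at or before 2 times median tmax of the respective treatment", followed by a note that the median is taken without the subjects who vomited. Data judged non-evaluable are left out of the statistical PK analysis.

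SAP section 6.3 builds the PK parameter set by removing parameters excluded for relevant protocol deviations or "because of non-evaluability, as described in Section 7.3.1 of the CTP". SAP section 7.4 adds: "All analyses based on the PKS are based on PK parameter values which are not flagged for exclusion". On who decides, SAP section 6.3 says that "the decisions on the allocation of subjects to analysis sets will be made at latest at the RPM", with a decision log.

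On route, protocol section 4.1.4 says: "Trial drug will be injected subcutaneously in the abdominal region or into the thigh". Its Table 4.1.4:1 shows the SC route for all four dose groups.

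SAP section 4 states: "All analyses described in this TSAP are in accordance with the statistical methods described in the CTP". It then corrects one item in the same protocol section 7.3.1, the reference to an undefined subject set RS, saying "this must be a typo in the CTP". It does not mention the emesis criterion.

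**The concern.** An emesis criterion of this form makes sense when vomiting can expel part of a swallowed dose and so spoil the measured exposure. Here the drug is injected under the skin, and the documents give no other reason for the criterion. It looks like template text for oral dosing; that origin is an inference.

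The data at risk are AUC0-tz and Cmax (primary) and AUC0-∞ (secondary) of a subject whose exposure is unaffected. Dose Group 1 is the shared reference, so a loss there would touch T1/R, T2/R and T3/R together, as any exclusion from that group would. An override is possible, but no text calls for one, and in this open-label trial it would be made with treatment known.

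**Working it through.** **1. Does the criterion apply as written?** Protocol 7.3.1 says that data meeting a listed criterion will be considered non-evaluable. SAP 6.3 cites that section without exception, SAP 7.4 analyses unflagged values only, and SAP 4 leaves the criterion untouched. It is therefore part of the plan.

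**2. Length of the window.** Protocol Table 1.2.5:3 gives median tmax of 7.0 and 6.0 days for the two SC groups of trial 1368.3. Taking these as a proxy (an assumption, since the actual window uses this trial's medians by treatment):

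- 2 × 6.0 = 12 days (288 h)
- 2 × 7.0 = 14 days (336 h)

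Vomiting from any cause in roughly the first two weeks would meet the criterion.

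**3. Reproducing the plan's precision figures.** Protocol Table 7.6:1 treats one comparison as two parallel arms of 12, with a two-sided 90% CI and 95% probability. With σ = √ln(1 + gCV²) and df = n₁ + n₂ − 2:

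precision = exp{ t(0.95, df) × σ × √(1/n₁ + 1/n₂) × √(χ²(0.95, df)/df) }

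For 12 v 12 this gives 1.2390, 1.2912 and 1.3444 at gCV 25%, 30% and 35%. At ratio 100% the limits are 80.71–123.90, 77.45–129.12 and 74.38–134.44, as in the table.

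**4. One subject lost from one arm (12 v 11, df = 21).**

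| gCV | 12 v 12 | 12 v 11 | Change | 90% CI at ratio 100%, 12 v 11 |
|---|---|---|---|---|
| 25% | 1.2390 | 1.2468 | 0.008 | 80.20–124.68 |
| 30% | 1.2912 | 1.3008 | 0.010 | 76.87–130.08 |
| 35% | 1.3444 | 1.3560 | 0.012 | 73.75–135.60 |

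The CI half-width on the log scale grows by a factor of 1.0292 in every row. For scale, the table's own precision differs by 0.105 between gCV 25% and 35%.

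**5. The same loss under the planned model.** Assume 12 matched sets, each holding one subject from each of the four groups. The figures are ratios of the standard error of an affected contrast to its value with complete data.

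- No within-set correlation, one loss: √[(1/12 + 1/11)/(1/12 + 1/12)] = 1.0225.
- No within-set correlation, two losses in one arm: √[(1/12 + 1/10)/(1/12 + 1/12)] = √1.1 = 1.0488.
- Set as a random effect with within-set correlation 0.3, 0.5 and 0.7 (assumed values, generalised least squares): 1.0266, 1.0280 and 1.0289 for one loss; 1.0577, 1.0607 and 1.0626 for two.
- Set as a fixed effect: 1.0299 for one loss and 1.0646 for two.

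A missing Dose Group 1 value gives the same ratio for all three contrasts. A missing T1 value leaves T2/R and T3/R at 1.0000.

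**6. How often?** The documents give no emesis rate, so the expected cost over the trial cannot be calculated.

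**The case against.** The strongest reply is that harm needs two events: a subject must vomit in the window, and the criterion must then be applied. The protocol's summaries of earlier trials mention nausea after repeated IV doses but report no vomiting. The list is introduced as examples, the SAP's table of important protocol deviations has no emesis code, and the Report Planning Meeting can keep the subject and record why. Exclusion works value by value, and the sponsor's PK procedure, which governs flagging, is not in the documents. The size shown above is the cost of losing any subject for any reason. The RS precedent is also imperfect: an undefined abbreviation can be called a typo, whereas this is a fully worded criterion whose removal changes the planned analysis.

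Most of this stands as a limit on importance. The trigger may never occur, actual flagging practice cannot be judged, and the loss is modest. It does not remove the defect. Giving examples leaves the list open to additions but does not weaken the items it names. The meeting may override, yet nothing tells it to, and doing so would be a case-by-case departure from a written criterion. The last objection bears on how the correction is worded, not on whether it is needed.

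**Conclusion.** The concern holds, as a minor point. The plan contains a PK exclusion criterion that does not fit subcutaneous dosing, and the SAP adopts it by reference. If it is triggered and not overridden, valid primary-endpoint values are lost.

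One loss costs 0.008 to 0.012 in precision over gCV 25% to 35%, or 2.2% to 3.0% in the standard error of an affected contrast. Two losses in one arm cost 4.9% to 6.5% in standard error. These figures assume complete data otherwise and, for the standard errors, 12 full sets of four. No bias is shown, and the trial aims at estimation with no acceptance range, so no planned decision turns on the loss. The case for change is that the criterion has no stated benefit here and is cheap to switch off in advance.

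**What to change.** Revise the SAP before the Report Planning Meeting:

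- **SAP section 4:** add one sentence, beside the RS correction, saying that the emesis criterion of protocol 7.3.1 does not apply because all dosing is subcutaneous. Word the general statement of accordance with the protocol so that it allows for this change.
- **SAP section 6.3:** repeat in the PK parameter set definition that emesis is not a ground for PK exclusion. Editing 6.3 alone would contradict section 4.
- **Protocol section 7.3.1:** delete the bullet at the next amendment. The approval requirements of protocol section 8.1 apply to amendments, so this need not be done separately; the SAP text is enough if no further amendment is made.

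Errors of administration or dose remain covered by deviation codes C2 and C3 in SAP Table 6.2:1. The cost is one sentence in each of the two SAP sections. Dosing, data collection and the care of subjects are unaffected.

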7.3.2 Secondary analyses

The same statistical model as stated in [Section 7.1.3](#) will be repeated for the primary and secondary endpoints but with all sources of variation considered as fixed effects.

Additionally, the pharmacokinetic parameters listed in [Section 5.5.1.3](#) will be calculated and analysed descriptively, if feasible.

7.3.3 Safety analyses

Safety will be assessed for the endpoints listed in [Section 5.2.1](#). All treated subjects (that is, all subjects who received at least one dose of study drug), will be included in the safety analysis. Safety analyses will be descriptive in nature and will be based on BI standards. No hypothesis testing is planned.

The analyses will be done by ‘treatment at onset’.

Treatments will be compared in a descriptive way. Tabulations of frequencies/proportions will be used for the evaluation of categorical (qualitative) data, and tabulations of descriptive statistics will be used to analyse continuous (quantitative) data.

Proprietary confidential information © 2019 Boehringer Ingelheim International GmbH or one or more of its affiliated companies

Measurements (such as ECG, vital signs, or laboratory parameters) or AEs will be assigned to treatments (see [Section 4.1](#)) based on the actual treatment at the planned time of the measurement or on the recorded time of AE onset (concept of treatment emergent AEs).

Therefore, measurements planned or AEs recorded prior to first intake of trial medication will be assigned to 'screening', those between first trial medication intake until end of the residual effect period (see [Section 1.2.5](#)) will be assigned to the treatment period. Events after the residual effect period but prior to next intake or end of trial examination will be summarized as 'follow-up'. The follow-up will be summarised according to previous treatment. These assignments including the corresponding time intervals will be defined in detail in the TSAP. AEs occurring after the last per-protocol contact but entered before database lock will be reported to drug safety only and will not be captured in the trial database.

Additionally, further treatment intervals (analysing treatments) may be defined in order to provide summary statistics for time intervals, such as combined treatments, on-treatment totals or periods without treatment effects (such as screening and post-study intervals).

Adverse events will be coded using the Medical Dictionary for Regulatory Activities (MedDRA). Frequency, severity and causal relationship of AEs will be tabulated by treatment, system organ class and preferred term. SAEs, AESIs (see [Section 5.2.2.1](#)) and other significant AEs (according to ICH E3) will be listed separately.

Laboratory data will be compared to their reference ranges. Values outside the reference range as well as values defined as clinically relevant will be highlighted in the listings. Additionally, differences from baseline will be evaluated.

Vital signs or other safety-relevant data observed at screening, baseline, during the course of the trial and at the end-of-trial evaluation will be assessed with regard to possible changes compared to findings before start of treatment.

Relevant ECG findings will be reported as AEs.

7.3.4 Interim analyses

No interim analysis is planned.

7.3.5 Pharmacokinetic analyses

The pharmacokinetic parameters listed in [Section 5.5.1](#) for drug BI 655130 will be calculated according to the relevant SOP of the Sponsor [[001-MCS-36-472](#)].

Individual plasma concentration data and the pharmacokinetic parameters will be tabulated, graphically displayed and summarized by descriptive statistics. The analysis of PK endpoints will be based on PKS.

Only concentration values within the validated concentration range and actual sampling times will be used for the calculation of pharmacokinetic parameters. Concentrations used in the pharmacokinetic calculations will be in the same format provided in the bioanalytical report, (that is, to the same number of decimal places provided in the bioanalytical report).

Proprietary confidential information © 2019 Boehringer Ingelheim International GmbH or one or more of its affiliated companies

If a predose concentration value is greater than 5% of C_{max} , the subject's pharmacokinetic data will be not included in any statistical evaluations, in accordance with international guidances. The individual pharmacokinetic parameters of such a subject will be calculated and listed separately. If a predose concentration is above BLQ, but less than or equal to 5% of the subject's C_{max} value, the subject's data without any adjustments will be included in all pharmacokinetic measurements and calculations.

7.4 HANDLING OF MISSING DATA

7.4.1 Safety

With respect to safety evaluations, it is not planned to impute missing values.

7.4.2 Plasma drug concentration - time profiles

Handling of missing PK data will be performed according to the relevant Corporate Procedure of the Sponsor [[001-MCS-36-472](#)].

Drug concentration data identified with NOS (no sample available), NOR (no valid result), NOA (not analysed), BLQ (below the lower limit of quantification), or NOP (no peak detectable) will be displayed as such and not replaced by zero at any time point (this rule also applies also to the lag phase, including the predose values).

7.4.3 Pharmacokinetic parameters

Handling of missing PK data will be performed according to the relevant SOP of the Sponsor [[001-MCS-36-472](#)].

For the non-compartmental analysis, concentration data identified with NOS, NOR or NOA will generally not be considered. Concentration values in the lag phase identified as BLQ or NOP will be set to zero. All other BLQ/NOP values of the profile will be ignored. The lag phase is defined as the period between time zero and the first time point with a concentration above the quantification limit.

7.5 RANDOMISATION

The study will not be randomised as individually matched subjects will be used. Thus, this section is not applicable.

7.6 DETERMINATION OF SAMPLE SIZE

It is planned to enter a total of $4*12 = 48$ subjects in the trial, because this sample size is considered sufficient to achieve the aims of this exploratory trial. With this sample size, the following precision in estimating the ratio of geometric means (test/reference) can be expected with 95% probability. Precision is defined as the ratio of upper CI limit to the relative BA estimate. Note that the precision is independent of the actual ratio of geometric means.

Proprietary confidential information © 2019 Boehringer Ingelheim International GmbH or one or more of its affiliated companies

The observed inter-individual geometric coefficient of variation (gCV) in a previous trial (1368.3) was roughly 30% for C_{max} and for AUC. For various assumptions on the gCV, [Table 7.6: 1](#) provides an overview of the precision for estimating the ratio of geometric means (test/reference). For illustrative purposes, the expected 90% confidence intervals are displayed for different values of the ratios T/R of geometric means.

Table 7.6: 1 Precision that can be expected with 95% probability and illustrative two-sided 90% confidence intervals around the ratios of geometric means (T/R) for different gCVs in a parallel trial (for one comparison based on 2 arms)

gCV [%]	Precision upper CL / relative BA estimate	Ratio [%] [*]	Lower CL [%]	Upper CL [%]
25	1.24	90	72.64	111.51
25	1.24	100	80.71	123.90
25	1.24	110	88.78	136.29
30	1.29	90	69.70	116.21
30	1.29	100	77.45	129.12
30	1.29	110	85.19	142.03
35	1.34	90	66.95	120.99
35	1.34	100	74.38	134.44
35	1.34	110	81.82	147.88

^{*}Ratio of geometric means (test/reference) for a PK endpoint is defined by $\exp(\mu_T)/\exp(\mu_R)$.

The 90% confidence interval limits in the table were derived by

$$CI\ limit_{upper,lower} = \exp(\ln(\theta) \pm \omega),$$

with θ being the ratio (T/R) on original scale and ω the distance from the estimate θ to either confidence interval limit on the log-scale, which was obtained from the achievable precision on the original scale.

The calculation was performed as described by Julius [\[R11-5230, Chapter 8\]](#) using R Version 3.4.2.

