AUC _{0-inf} [μ g·day/mL]	127 (6.05)	563 (26.2)	1260 (6.81)	3380 (15.6)	5080 (18.9)	
C _{max} [μ g/mL]	6.63 (3.28)	20.3 (13.6)	60.6 (7.17)	153 (12.7)	235 (2.79)	

Proprietary confidential information © 2019 Boehringer Ingelheim International GmbH or one or more of its affiliated companies

In the MRD Trial 1368.2, PK data are consistent with the preceding single dose study as shown in [Table 1.2.5:2](#).

Table 1.2.5:2 Geometric mean (geometric CV %) PK parameters of BI655130 in study 1368.2 after multiple dosing

Dose	N=6 [Day 1] 0-168 h	N=6 [Day 8] 168-336 h	N=6 [Day 15] 336-504 h	N=6 [Day 22] 504-672 h
AUC _{0-t} (μg·day/mL)	298 (9.26)	451 (7.96)	604 (4.77)	760 (4.21)
C _{max} (μg/mL)	77.9 (19.4)	101 (11.4)	117 (14.8)	141 (4.33)
Dose	N=6 [Day 1] 0-168 h	N=6 [Day 8] 168-336 h	N=6 [Day 15] 336-504 h	N=6 [Day 22] 504-672 h
AUC _{0-t} (μg·day/mL)	552 (10.4)	895 (4.45)	1140 (5.11)	1390 (4.63)
C _{max} (μg/mL)	130 (8.48)	185 (9.31)	223 (6.64)	253 (8.70)
Dose	N=6 [Day 1] 0-168 h	N=6 [Day 8] 168-336 h	N=6 [Day 15] 336-504 h	N=6 [Day 22] 504-672 h
AUC _{0-t} (μg·day/mL)	923 (17.3)	1610 (18.0)	2090 (16.9)	2500 (16.7)
C _{max} (μg/mL)	229 (22.9)	310 (21.9)	444 (34.1)	467 (21.4)
Dose	N=5 [Day 1] 0-168 h	N=5 [Day 8] 168-336 h	N=4 [Day 15] 336-504 h	N=4 [Day 22] 504-600 h
AUC _{0-t} (μg·day/mL)	1770 (12.5)	2900 (7.52)	3950 (16.1)	4660 (12.9)
C _{max} (μg/mL)	422 (18.5)	646 (10.7)	780 (17.1)	826 (15.8)

Exposure of both dose groups is in the linear dose range. The geometric mean t_{1/2} values after dose 4 were similar across dose groups and ranged from 26.5 to 33.5 days with no dose dependency.

[Table 1.2.5:3](#) summarizes PK data of the recent completed clinical study 1368.3 conducted according to a parallel (matched) group design. Bioavailability of the SC injection was calculated to be about 50% and of the SC injection 70% using the IV group as reference.

Proprietary confidential information © 2019 Boehringer Ingelheim International GmbH or one or more of its affiliated companies

Table 1.2.5:3 Geometric mean (geometric CV %) PK parameters of BI655130 in study 1368.3 after a single dose

Dose	N=11 [SC]	N=12 [SC]	N=11 [IV]
AUC _{0-inf} ($\mu\text{g}\cdot\text{day}/\text{mL}$)	574 (40.1)	1600 (29.5)	2280 (16.0)
C _{max} ($\mu\text{g}/\text{mL}$)	12.2 (44.5)	33.4 (32.7)	114 (18.0)
T _{max} ¹ (day)	0.3 - 14 7.0	4 - 21 6.0	0.02-0.3 0.13
t _{1/2} (day)	20.6 (26.7)	25.6 (23.5)	27.1 (17.1)

¹min – max, median

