3. DESCRIPTION OF DESIGN AND TRIAL POPULATION

3.1 OVERALL TRIAL DESIGN AND PLAN

This study will explore the relative bioavailability, safety, and tolerability following a subcutaneous (SC) injection of BI 655130 at different dose strengths, injection volumes, and injection sites:

- One SC injection of periumbilical (Dose Group 1)
- Two SC injections of each periumbilical left and right (Dose Group 2)
- Two SC injections of each periumbilical left and right (Dose Group 3)
- One SC injection of in the thigh (Dose Group 4)

The total dose in Dose Group 1, 2, and 4 is of BI 655130 and the total dose in Dose Group 3 is of BI 655130.

The study will be conducted in a single-dose, open-label, matched-group design. The exposure in Dose Group 1 will be used as reference to assess the relative bioavailability of Dose groups 2 - 4. For details refer to [Section 4.1](#).

The study will start with Dose Group 1 and 2. After completion of treatment of the first two dose groups, the study will continue with Dose Group 3 and 4. At any time during the ongoing study, further dosing will be stopped in case of safety and tolerability concerns based on the pre-specified trial-specific stopping criteria ([Section 3.3.4.2](#)).

The Dose Group 3 will follow a staggered administration with treatment of 6 subjects (cohort A) in the first week and the remaining subjects (cohort B) from Week 2.

A documented Safety Review of Dose Group 1 and 2 at least 10 days after last dosing in Dose Group 2 must take place prior to continue the study with Dose Groups 3 and 4. An unscheduled safety review meeting can be requested anytime for any reasonable cause by the Principal Investigator (or an authorised deputy) or the sponsor of the study, e.g. because of any unforeseen adverse events. Continuation of the study will only be permitted if no safety concerns exist in the opinion of the Principal Investigator (or an authorised deputy) and the trial clinical monitor (or an authorised deputy). In addition, at least 8 evaluable subjects in each of the Dose Group 1 and 2 are required to decide about continuation with the remaining dose groups.

The minimum data set for review consists of the following data:

- AEs (including clinically relevant findings from ancillary safety testing listed below)
(Note: AEs may be ongoing at the time of Safety Reviews and AE information may be subject to change prior to Database Lock)
- Vital signs
- Clinical laboratory tests

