5.5.1 Pharmacokinetic endpoints

5.5.1.1 Primary endpoints

The following primary endpoints will be determined for BI 655130:

- AUC_{0-tz} (area under the concentration-time curve of the analyte in plasma over the time interval from 0 to the last quantifiable data point)
- C_{max} (maximum measured concentration of the analyte in plasma)

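### Is the planning gCV of roughly 30% in Section 7.6 too low, given the SC-arm Cmax values from trial 1368.3?

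*Protocol*

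**What the plan says.** Protocol Section 7.6 fixes the size ("It is planned to enter a total of $4*12 = 48$ subjects in the trial") and justifies it by expected precision, defined as the upper confidence limit divided by the point estimate. The input is one figure: "The observed inter-individual geometric coefficient of variation (gCV) in a previous trial (1368.3) was roughly 30% for" Cmax and for AUC. The section then moves to a table, introduced with "For various assumptions on the gCV" and titled "Precision that can be expected with 95% probability and illustrative two-sided 90% confidence intervals". Its rows are gCVs of 25, 30 and 35%, with precision 1.24, 1.29 and 1.34, for one comparison of two parallel arms.

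The earlier trial is summarised in Table 1.2.5:3 (geometric mean, with gCV in %):

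| 1368.3 arm | AUC0-inf | Cmax |
|---|---|---|
| SC, N = 11 | 574 (40.1) | 12.2 (44.5) |
| SC, N = 12 | 1600 (29.5) | 33.4 (32.7) |
| IV, N = 11 | 2280 (16.0) | 114 (18.0) |

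Section 7.2 sets two-sided 90% confidence intervals ("This method corresponds to the two one-sided t-tests procedure, each at the 5% significance level"). It states no acceptance range and tests no hypothesis.

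**The concern.** All four groups of this trial receive SC injections, so the SC arms of 1368.3 are the natural source for a planning gCV. For Cmax, a primary endpoint, 30% is below both of them. For AUC it matches one arm and is well below the other. Section 7.6 does not say which arm, or what pooling, produced the figure, and the table ends below three of the candidate values: 38.7% (both SC arms pooled, Cmax), 40.1% and 44.5%.

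Table 1.2.5:3 also reports AUC0-inf, whereas the primary endpoint is the "area under the concentration-time curve of the analyte in plasma over the time interval from 0 to the last quantifiable data point", whose gCV in 1368.3 is not given.

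Table 7.6:1 is the only quantitative support for 12 per group. If its input were too favourable, the trial could deliver wider intervals for Cmax than its readers were led to expect.

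**Working it through.** **1. Reproduce the table.** With n = 12 per arm and df = 22:

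- σ = √ln(1 + gCV²)
- ω = t(0.95, df) × σ × √(2/12) × √(χ²(0.95, df)/df)
- precision = exp(ω); limits = ratio × exp(±ω)

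At 22 df, t = 1.7171 and χ² = 33.924, so ω = 1.7171 × 0.4082 × 1.2418 × σ = 0.8705σ. At 30%, σ = 0.2936, ω = 0.2555 and precision = 1.2912. At 25% and 35% the results are 1.2390 and 1.3444. All 18 confidence limits agree to two decimals, so the table's arithmetic is right.

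**2. Which arm of 1368.3 is relevant?** Doses are redacted. Section 1.2.5 says "Bioavailability of the SC injection was calculated to be about 50% and of the SC injection 70% using the IV group as reference". Since 1600/2280 = 70% and 2 × 574/2280 = 50%, the higher-exposure SC arm appears to share the IV dose, and the other SC arm to have had about half of it. Section 3.1 gives three of the present groups one total dose ("The total dose in Dose Group 1, 2, and 4 is of BI 655130"). Section 4.1.3 describes a separate highest dose. Appendix 10.1 lists four vials for Dose Group 3 and two for each of the others. On this reading the higher-exposure arm is probably the match for Dose Groups 1, 2 and 4, and no group has the lower arm's total dose. This is inference, not a documented fact.

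**3. Pooled SC values.** Weighting the log variances by 10 and 11 df:

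- Cmax: (10 × 0.1807 + 11 × 0.1016)/21 = 0.1392, so gCV = 38.7%
- AUC0-inf: (10 × 0.1491 + 11 × 0.0834)/21 = 0.1147, so gCV = 34.9%

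**4. Precision at each candidate value.** The 33 df column uses the four-group model of Section 7.1.3 with 12 matched sets of four: 48 − 4 − 11 = 33 df, t = 1.6924, χ² = 47.400, ω = 0.8280σ. It assumes that matching removes no variance.

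| gCV | Source | 22 df | 90% CI at ratio 100% (22 df) | 33 df |
|---|---|---|---|---|
| 29.5% | AUC0-inf, higher SC arm | 1.286 | 77.77–128.59 | 1.270 |
| 30% | Section 7.6 | 1.291 | 77.45–129.12 | 1.275 |
| 32.7% | Cmax, higher SC arm | 1.320 | 75.77–131.98 | 1.302 |
| 34.9% | AUC0-inf, SC pooled | 1.343 | 74.47–134.29 | 1.324 |
| 38.7% | Cmax, SC pooled | 1.384 | 72.26–138.38 | 1.362 |
| 40.1% | AUC0-inf, lower SC arm | 1.400 | 71.45–139.95 | 1.377 |
| 44.5% | Cmax, lower SC arm | 1.448 | 69.07–144.78 | 1.422 |

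**5. How much matching would close the gap?** Section 3.3 matches individually on gender and on body weight within 10%. At 33 df, the share of log variance that matching must explain is 1 − (ln target / ln precision)².

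- 32.7% back to 1.2912: 1 − (0.2555/0.2639)² ≈ 6%
- 38.7% back to 1.3444, the 35% row: 1 − (0.2959/0.3090)² ≈ 8%

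The documents give no within-set variance, so these are thresholds, not predictions.

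**The case for a change.** The strongest case for a change is that, in an estimation trial, expected precision is the design justification, so its input should be traceable. It is not. The higher SC arm rounds to about 30%. Pooling all three arms, including the low-variance IV arm, gives 29.9% for AUC0-inf and 33.2% for Cmax. Pooling the SC arms alone gives 34.9% and 38.7%. A reader cannot tell which was used.

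The dose match is inferred, and a gCV of 32.7% from 12 subjects has a 95% interval of about 23–58% (chi-square on the log variance, 11 df). A ceiling of 35% therefore shows little of the plausible upside. Naming the arm and adding rows would cost very little.

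The missing source is real, and so is the rounding down of Cmax from 32.7%. The rest carries less weight. Every arm's gCV is already printed in the same protocol, and each table row is conditional on its assumed gCV. The wide interval is common to any gCV from a dozen subjects and also reaches below 30%. The largest figures, 1.40 and 1.45, need the lower-exposure arm to apply and an unmatched two-arm analysis, which is not the planned one.

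**Conclusion.** The concern does not require a change. No stated figure is shown to be wrong: the table reproduces exactly, and one rough value for two endpoints is a fair summary of the higher-exposure SC arm. For that arm, Cmax precision moves from 1.29 to 1.32 on the table's basis, or is 1.30 under the planned model before any benefit from matching. Both lie within what the 35% row already shows (1.34).

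The gap would be material only if Cmax variability were nearer the pooled SC value (1.38, or 1.36 at 33 df) or the lower arm (1.45, or 1.42). Even then no decision turns on it. Section 7.6 calls the trial exploratory and Section 7.2 sets no acceptance range, so there is no threshold to miss. The confidence intervals in the report will reflect the variability actually observed, whatever gCV was assumed at planning.

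This rests on two assumptions: the inferred dose match, and complete matched sets for the 33 df figures. The AUC0-tz variability in 1368.3 cannot be checked from the documents, so the 30% for that endpoint is neither confirmed nor contradicted. What remains is an unnamed source arm, an editorial omission with no effect on the sample size, the estimates or the analysis.
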